## 1. Abstract

a. Provide no more than a one page research abstract briefly stating the problem, the research hypothesis, and the importance of the research.

Distal pancreatectomy (DP) is an operation performed for benign, premalignant and malignant disease of the pancreas. With recent advances in the operative and perioperative care of patients undergoing PD, the operative mortality of the procedure has been reduced to less than 1% in highvolume centers. However, post-operative complications still occur in approximately 30-50% of patients. The most common complication after distal pancreatectomy is leakage from the remnant gland or a pancreatic fistulae (PF). In order to identify and treat PF earlier, most surgeons routinely drain the abdominal cavity after DP. However the optimal drain for routine drainage is unknown.

We hypothesize that closed suctioning drains may contribute to the development and/or prolongation of PF because of high negative pressures. Therefore, we propose a project comparing closed suctioning drains versus closed non-suctioning. The primary aim of this study is to test the hypothesis that non-suctioning drains will lead to fewer clinically significant PF and infectious complications after DP.

## 2. **Objectives** (include all primary and secondary objectives)

The primary endpoints of the study will be the development of POPF, as recently defined and graded by the International Study Group of Pancreatic Surgery (ISGPS).

Secondary endpoints will include length of hospital stay, need for enteral or parenteral nutrition, need for radiologic or surgical intervention, septic complications, and perioperative mortality.

**3. Background** (briefly describe pre-clinical and clinical data, current experience with procedures, drug or device, and any other relevant information to justify the research)

Prophylactic drainage of the abdominal cavity is frequently utilized by surgeons to prevent intra-peritoneal collections of blood, bile, chyle, pancreatic, biliary and gastrointestinal juices. The collections, particularly bile and pancreatic fluid can become infected and are potentially caustic to adjacent tissue and structures. Additionally, many surgeons believe that prophylactic drains are useful in detecting complications early, and early intervention can prevent the development of higher degrees of complications.

To date, all studies evaluating drainage following pancreatic resection have focused primarily on pancreaticoduodenectomy and have compared closed suction drains to no drainage. Pancreatic fistula develop in approximately 30% of patients undergoing distal pancreatectomy and 20% will be clinically significant. Although the only RCT to date from MSKCC comparing closed suction drainage to no drainage following pancreatic resection was a negative trial, only 40 of these patients had a distal pancreatectomy, all had closed suction drains placed and it was inadequately powered to detect a difference. Importantly, another study from MSKCC demonstrated very high pressure gradients generated by 3 different types of closed suction systems which vary based on the fullness of the system and when "stripped" reach levels as high as - 225mmHg. We theorize that high negative pressure could contribute to the development or prolongation of complications and leakage from the pancreatic remnant.

Despite evidence-based data questioning the utility of routine drainage in pancreatic surgery, most surgeons around the world and at Johns Hopkins still routinely drain the pancreatic transection margin following distal pancreatectomy with closed suction drains. However, some surgeons have abandoned closed suction drains for closed non-suctioning drains which function by draining to gravity pressure. These drains still prevent fluid collections and allow for early detection of complications but do not generate the same high negative pressures. Clearly the optimal drain to drain the peritoneal cavity following distal pancreatectomy is still unclear for the majority of pancreatic surgeons.

## 4. Study Procedures

a. Study design, including the sequence and timing of study procedures (distinguish research procedures from those that are part of routine care).

Head-to-head Prospective Randomized Trial: At operation, consented patients will be randomized after removal of the DP specimen to either drain with a single closed suctioning Jackson Pratt versus a closed non-suctioning straight drain. Patients will be stratified based on the surgeon's assessment of the gland texture, as hard versus soft. All drains will be positioned near the pancreatic transection margin. Recorded variables at the time of surgery will include pancreatic gland texture, pancreatic duct diameter, blood loss, and intraoperative time.

Since both types of drains are currently used by surgeons at JHH, we believe that there is no significant change to what is considered routine care of these patients. Surgeon preference currently dictates the drain choice at the time of operation.

b. Study duration and number of study visits required of research participants.

Our plan is to randomize 134 pts per arm (268 total). Approximately 115 DPs are performed annually at JHH. Based on a patient recruitment rate of 90%, the estimated period to complete this trial will be 31 months.

The endpoints of the study are events noted in the 90-day postoperative period, therefore no additional study visits will be required for the study participants, other that their postoperative hospital stay and routine postoperative visits. A case report form (Appendices Section) will be used to facilitate routine collection of standardized information from every subject in order to reliably detect and grade POPF and other complications. This form will be completed by the study coordinator on the day of discharge +/- one day, on the day of re-discharge (in case of readmission) +/- one day, on the day of any postoperative outpatient visit +/- one day, and at 90 days from surgery +/- two weeks. This information will be collected either over the telephone.or in person (eg, in the hospital inpatient setting or at ordinary, outpatient, patient-care clinic visits).

c. Blinding, including justification for blinding or not blinding the trial, if applicable.

This will not be a blinded trial.

d. Justification of why participants will not receive routine care or will have current therapy stopped.

Participants in both groups will receive standard surgical and post-surgical care.

e. Justification for inclusion of a placebo or non-treatment group.

Both study groups will receive standard treatment (DP) for their pancreatic pathology.

f. Definition of treatment failure or participant removal criteria.

Treatment failure is defined as the development of any condition that poses identifiable risk to participant safety, or the incidence of POPF at significantly higher rate that the control group.

g. Description of what happens to participants receiving therapy when study ends or if a participant's participation in the study ends prematurely.

Patients will continue to receive standard post-operative care if their participation in the study ends prematurely, or after the study ends.

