## **Study Statistics**

a. Primary outcome variable.

The primary endpoints of the study will be the development of POPF, as recently defined and graded by the International Study Group of Pancreatic Surgery.

b. Secondary outcome variables.

Secondary endpoints will include length of hospital stay, need for enteral or parenteral nutrition, need for radiologic or surgical intervention, septic complications, and perioperative mortality.

c. Statistical plan including sample size justification and interim data analysis.

The incidence of either POPF after DP is approximately 30%, based on retrospective studies validating the ISGPS definition. A clinically significant reduction of the event rate to 15% in the treatment group would require enrollment of 134 patients per arm (268 total), assuming a 2-tailed test with  $\alpha$  of 0.05 and power of 0.80. We therefore plan to consent and enroll 300, accrue 270 (roughly 90% of 300).

Interim analysis will be performed after recruitment and analysis of 150 patients.

d. Early stopping rules.

The trial will be terminated prematurely, if statistically significant differences between the groups or potential safety risks are identified.

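### Randomisation is stratified by gland texture but the planned analysis ignores it; a texture-stratified primary test is a small, nearly free gain in power

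*Combined protocol and SAP*

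**What the plan says.** Section 4a (Study Procedures) places randomisation in the operating room: "consented patients will be randomized after removal of the DP specimen". The next sentence reads "Patients will be stratified based on the surgeon's assessment of the gland texture, as hard versus soft". It does not use the word randomisation, but its position makes stratified randomisation the natural reading. Texture is also captured as data: "Recorded variables at the time of surgery will include pancreatic gland texture, pancreatic duct diameter, blood loss, and intraoperative time".

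Study Statistics is the only statistical section. The primary outcome is POPF by the ISGPS definition, treated as a yes/no event for the sample size. A fall from 30% to 15% "would require enrollment of 134 patients per arm (268 total), assuming a 2-tailed test", with alpha 0.05 and power 0.80. No primary test is named, and neither texture, strata nor adjustment is mentioned.

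On monitoring, the section says "Interim analysis will be performed after recruitment and analysis of 150 patients" and then "The trial will be terminated prematurely, if statistically significant differences between the groups or potential safety risks are identified". It does not say which test decides significance.

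**The concern.** Texture is the only stratification factor, which suggests the investigators expect it to matter for POPF. If it does, part of the variation in outcome is between textures. An unstratified test counts that variation as noise, although a design balanced within texture has already removed it from the treatment comparison. The standard error is then too large, the true type I error falls below 5%, and power is lost. If the arms are not balanced within texture (the protocol does not mention blocking), the unstratified test keeps its 5% level but loses more power relative to the stratified one.

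There is also a question of pre-specification. The trial is unblinded and can stop on a significant difference at 150 patients. Stratified and unstratified tests of the same data can fall on opposite sides of 0.05, and the plan does not say which one counts.

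**Working it through.** **1. The plan's own figure.** Inputs from Study Statistics (c): 30% versus 15%, two-sided alpha 0.05, power 0.80. The mean rate is 0.225.

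- Uncorrected: n = [1.960·√(2·0.225·0.775) + 0.842·√(0.30·0.70 + 0.15·0.85)]² / 0.15² = 120.5, so 121 per arm.
- Continuity-corrected: n′ = (n/4)·[1 + √(1 + 4/(n·0.15))]² = 133.5, so 134 per arm.

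The stated 134 is therefore the continuity-corrected, unstratified two-proportion calculation. At 134 per arm the formulas give 80.2% power with the correction and 84.0% without.

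**2. Assumptions the documents do not supply.** The share of soft glands is taken as 50%, then 70%. The soft/hard odds ratio (OR) for POPF is 1, 2, 3, 5 or 9. Overall rates are held at 30% and 15% with a common treatment odds ratio across textures. At OR 3 the control rates are 41.1% (soft) and 18.9% (hard); at OR 9 they are 50.0% and 10.0%. The treatment odds ratio that gives 15% overall runs from 0.412 (OR 1) to 0.355 (OR 9).

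**3. Tests compared.** Pooled two-proportion z-test versus CMH, both two-sided at 0.05 without continuity correction. In stratum k, with m₁ and m₂ patients per arm, N = m₁ + m₂, t events in total and a events in arm 1, CMH uses z = |Σ(a − t·m₁/N)| / √Σ[m₁m₂t(N − t)/(N²(N − 1))]. Results come from simulation with 400,000 trials per scenario (800,000 for the extra-patient figures).

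**4. Final analysis, 134 per arm, half soft, balanced within texture (67 + 67 per arm).**

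| Soft/hard OR | Power, unstratified | Power, CMH | Alpha, unstratified | Alpha, CMH |
|---|---|---|---|---|
| 1 | 84.8% | 84.6% | 5.0% | 5.0% |
| 2 | 84.9% | 85.1% | 4.7% | 5.0% |
| 3 | 85.4% | 86.2% | 4.4% | 5.0% |
| 5 | 85.8% | 87.6% | 3.8% | 5.0% |
| 9 | 86.7% | 89.6% | 3.0% | 5.0% |

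To match CMH, the unstratified test would need about 10, 16 and 28 more patients in total at OR 3, 5 and 9.

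Hand check of the alpha column at OR 9: the pooled variance is 0.30·0.70 = 0.21, and the average within-texture variance is (0.50·0.50 + 0.10·0.90)/2 = 0.17. The effective cut-off is 1.96·√(0.21/0.17) = 2.18, a two-sided level of about 2.9%, in line with the simulated 3.0%.

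**5. Sensitivity: gain from CMH in power points at OR 1, 2, 3, 5 and 9.**

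- 70% soft, balanced (94 + 40 per arm): −0.3, 0.1, 0.5, 1.0, 1.6.
- Half soft, simple randomisation within texture: −0.3, 0.4, 1.4, 2.9, 4.9, with both tests at about 5.0% alpha.
- Continuity correction on both tests, half soft, balanced, OR 3: 81.2% versus 82.5%, so the gain is slightly larger.

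**6. Interim at 150 patients.** Assuming two-sided 0.05 and 30% versus 15%, the two tests give different verdicts in 0.2%, 1.8% and 5.9% of trials at OR 1, 3 and 9 if balanced, and in 2.1%, 6.7% and 12.6% if allocation within texture is unblocked.

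**The case against.** The strongest reply is that nothing goes wrong if texture is left out. Planned power is 80%, and the unstratified test stays above that in every scenario, at about 84.5% or more uncorrected and at least 80.6% corrected. The gain is a fraction of a point at OR 2 to 3, and the larger figures need OR 9, some of them with unblocked allocation as well. All of this is true, and it is why the point is one of efficiency and not of validity.

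Second, the sizing used a continuity correction, while the comparison above and the proposed test do not. Dropping the correction is the larger change: at OR 3 it moves the unstratified test from about 81.2% to 85.2%, and stratifying then adds about 0.8 points. That is a fair call for transparency. It does not weaken the case for stratifying, because with the correction on both sides the stratified test still gains.

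Third, the plan names no test, so it does not exclude a stratified one, and logistic regression with texture would serve much as CMH does. That also stands. The wider gap is the missing primary test, and the remedy here closes both.

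Fourth, the more serious interim problem is stopping on significance with no boundary or alpha adjustment. This is correct, but it is a separate matter that the choice of test does not solve.

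**Conclusion.** The concern holds. The trial stratifies by texture and records it, and the statistical section does not use it. A texture-stratified test keeps the 5% level and, with half the glands soft and balanced strata, adds about 0.8 points of power at a soft/hard odds ratio of 3, 1.8 at 5 and 2.9 at 9. The gain is smaller with 70% soft and larger if allocation within texture is unblocked. The downside is about 0.3 points if texture carries no information. These sizes rest on an assumed soft share, assumed odds ratios and a common treatment odds ratio, none of which the documents give. The change is worth making because it is nearly free and settles which test decides the trial. Omitting texture does not inflate type I error, and 134 per arm needs no revision.

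**What to change.** Add to Study Statistics (c):

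> The primary comparison of POPF between arms is a two-sided Cochran-Mantel-Haenszel test, without continuity correction, stratified by the gland texture (hard or soft) recorded at randomisation. The stratified risk difference is reported with its 95% confidence interval. The interim analysis at 150 patients uses the same test.

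Name the weights for the risk difference (Mantel-Haenszel weights would fit) and its variance method. State openly that the sample size used a continuity correction and the test does not; the uncorrected CMH test holds its level at 5.0% in the scenarios above. Keep 134 per arm.

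The cost is a few lines of wording, with no added data and no added patients. The change does not set an interim significance level, which has to be dealt with separately.

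### No primary analysis model for POPF is named, and neither gland texture (the stratification factor) nor the recorded duct diameter has a stated role in the analysis

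*Combined protocol and SAP*

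**What the plan says.** Section 4a (Study design) fixes the order of events in theatre: "consented patients will be randomized after removal of the DP specimen". On stratification it says: "Patients will be stratified based on the surgeon's assessment of the gland texture, as hard versus soft". On data it says: "Recorded variables at the time of surgery will include pancreatic gland texture, pancreatic duct diameter, blood loss, and intraoperative time". It does not say whether duct diameter is measured before or after the arm is known.

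Study Statistics a gives the endpoint: "The primary endpoints of the study will be the development of POPF, as recently defined and graded by the International Study Group of Pancreatic Surgery". Study Statistics c is the whole statistical plan. It takes the control rate from earlier work ("The incidence of either POPF after DP is approximately 30%, based on retrospective studies validating the ISGPS definition") and says that a fall to 15% "would require enrollment of 134 patients per arm (268 total), assuming a 2-tailed test" at a significance level of 0.05 and power of 0.80. It then gives an accrual target and one interim analysis after 150 patients.

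No primary test, model, covariate or effect measure is named. Nothing says that the analysis will account for texture, and no use is given for duct diameter.

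**The concern.** Two separate things are at stake.

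**Efficiency.** Texture and duct diameter are features of the gland that the drain cannot change, and both can be recorded at the transection margin before allocation. If they predict POPF, a model that includes them narrows the interval for the drain effect without adding patients. Texture was thought important enough to stratify on, and an analysis would normally reflect that. Duct diameter is not a stratification factor, so stratified randomization does not balance it directly.

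**Pre-specification.** Four intraoperative variables will be on file and no rule says which may enter a model. Two of them, blood loss and operative time, can go on accruing after randomization, because randomization follows specimen removal. The plan does not separate these from the two gland characteristics. The trial is unblinded (section 4c), has an interim look, and may stop on a statistically significant difference (Study Statistics d). Covariates chosen later could therefore be chosen by people who know the arms and the interim result.

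**Working it through.** **1. The plan's own figure.** Inputs from Study Statistics c: p1 = 0.30, p2 = 0.15, difference d = 0.15, mean 0.225, two-sided 0.05 (z = 1.960), power 0.80 (z = 0.842).

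- Uncorrected: n = [1.960 × √(2 × 0.225 × 0.775) + 0.842 × √(0.30 × 0.70 + 0.15 × 0.85)]² / 0.15² = [1.960 × 0.5906 + 0.842 × 0.5809]² / 0.0225 ≈ 120.5, so 121 per arm.
- Continuity-corrected: (120.5/4) × [1 + √(1 + 4/(120.5 × 0.15))]² ≈ 133.5, so **134 per arm**, an exact match.
- Variants that do not match: unpooled variance 118; one-sided 95, or 108 with the correction.

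The sample size therefore rests on an unadjusted comparison of two proportions. By the uncorrected approximation, power at 134 per arm is Φ[(0.15 × √134 − 1.960 × 0.5906) / 0.5809] = Φ(0.997) = 0.84, which is above the stated 0.80.

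**2. What adjustment could add.** The documents give no association between duct diameter and POPF, so the odds ratio per SD is an assumption, taken over a range. The covariate is standard normal, and the logistic model is calibrated so that the marginal rates stay at 30% and 15%. R² is the share of outcome variance explained, averaged over the arms.

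- Extra-patient equivalent = 268 × (1/(1 − R²) − 1).
- Narrowing of the interval = 1 − √(1 − R²).

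| Assumed OR per SD | R² | Extra-patient equivalent | Narrower CI |
|---|---|---|---|
| 1.25 | 0.0083 | 2 | 0.4% |
| 1.5 | 0.0267 | 7 | 1.3% |
| 2.0 | 0.0727 | 21 | 3.7% |
| 2.5 | 0.118 | 36 | 6.1% |

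**3. Simulated power at 134 per arm.** This compares the uncorrected two-proportion test with a logistic model adjusted for the one covariate, in sets of simulated trials at 30% versus 15%. Each cell is unadjusted then adjusted power.

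| Assumed OR per SD | Set A (6,000 trials) | Set B (6,000) | Set C (4,000) | Gain in points |
|---|---|---|---|---|
| 1.0 | 0.853, 0.853 | – | 0.859, 0.858 | about 0 |
| 1.25 | 0.848, 0.851 | – | – | 0.3 |
| 1.5 | 0.842, 0.853 | 0.853, 0.859 | 0.842, 0.854 | 0.6 to 1.2 |
| 2.0 | 0.845, 0.870 | 0.847, 0.866 | 0.846, 0.867 | 1.9 to 2.5 |
| 2.5 | 0.846, 0.893 | 0.851, 0.884 | 0.842, 0.887 | 3.3 to 4.7 |

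The Monte Carlo standard error of one estimate from 6,000 trials is √(0.85 × 0.15/6,000) = 0.0046, so differences below about one point are not distinguishable from noise. Type I error stayed near 5% (0.050 to 0.056). With texture also in the model, the gain was 0 to about 3 points.

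**4. Chance imbalance.** The SD of the difference in mean duct size between arms is √(2/134) = 0.12 SD. An imbalance of that size moves the POPF difference by about 0.5, 0.8, 1.3 or 1.7 percentage points at odds ratios of 1.25, 1.5, 2.0 or 2.5. The target difference is 15 points, and its standard error is √((0.21 + 0.1275)/134) = 0.050, or about 5 points.

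**The case against.** The strongest reply is that nothing here is wrong, and most of it stands.

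- A reader might infer that the plan commits to a bare two-proportion test. It does not. That form is inferred from the sample size, and the accurate statement is that the primary analysis is unspecified.
- A reader might infer that baseline risk information is thrown away. Texture is used in the randomization, and silence about duct diameter in a short plan does not show that it will be ignored.
- A reader might infer that imbalance in duct size would bias the result. Under randomization the unadjusted test's error rate already allows for chance imbalance, and the shifts in step 4 are small beside the standard error.
- The documents do not say that duct diameter predicts POPF, that it will be obtained in every patient, or when it is measured. A visible gain needs an odds ratio of 2.0 or more per SD, and every simulated unadjusted power already exceeds 0.80.
- The single-covariate figures in steps 2 and 3 are not the increment of duct diameter over texture. That increment is smaller if the two are correlated.

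What the reply does not remove is the gap itself. The stratification factor and a recorded gland characteristic have no analysis role, and no rule keeps variables that accrue after allocation out of a later model. The simulations show almost no loss when the covariate is useless.

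**Conclusion.** The point holds as an efficiency and pre-specification improvement, not as an error. Study Statistics c names no primary analysis model, and it gives neither texture nor duct diameter a role. The documents do not support reading this as a validity flaw or a shortfall in power: an unadjusted test is valid, 134 per arm reproduces exactly, and the stated power is met without adjustment.

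The size depends on an assumption. For odds ratios of 1.0 to 2.5 per SD of duct diameter, the power gain is about 0 to 4 points, and 0 to about 3 with texture also in the model. The lower end applies if duct diameter is weakly prognostic. The simulations tested the arm term in a logistic model, so they indicate the gain for a standardised risk difference and do not measure it directly. The case for naming the covariates in advance does not depend on the size of the gain.

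**What to change.** - **Study Statistics c.** Make the primary POPF analysis a logistic model with arm, gland texture and duct diameter, with the form of duct diameter stated (for example continuous on the log scale). Report the standardised (marginal) risk difference with its 95% CI. Give the unadjusted difference as a sensitivity analysis.
- **Section 4a.** Have duct diameter entered together with the texture call before the arm is revealed. Impute a missing value by a stated rule that ignores arm, such as the overall median, so that no patient is dropped.
- **Both places.** State that blood loss and operative time are descriptive, because they can accrue after allocation, and will not be adjusted for.

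The planned rates imply about 134 × 0.30 + 134 × 0.15 = 60 events, which is ample for a model with three terms.

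The cost is a few sentences in the plan and one ordering rule on the intraoperative form, with no new variables and no new patients. The downsides are that the model must be fixed before the interim look at 150 patients, and that the gain is close to nil if duct diameter is only weakly prognostic.

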#### 10. Costs

a. Detail costs of study procedure(s) or drug (s) or substance(s) to participants and identify who will pay for them.

The costs of this study are mainly administrative. These include salary support for the study coordinator and conference-related expenses for the investigators. No additional staff will be acquired for this project. We will attempt to obtain intramural funding to cover these expenses. The cost of perioperative care of patients undergoing DP at the Johns Hopkins Hospital are not expected to differ between the treatment and control groups. Some surgeons use suctioning drains and other use non-suctioning drains; therefore on average this trial is expected to result in no additional cost.

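### Open-label trial: the plan does not say who grades the primary endpoint (ISGPS POPF) and does not mask the arm when it is graded

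*Combined protocol and SAP*

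**What the plan says.** The endpoint (Study Statistics, item a): "The primary endpoints of the study will be the development of POPF, as recently defined and graded by the International Study Group of Pancreatic Surgery".

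How it is captured (section 4b): one standardised case report form is used for every subject, "in order to reliably detect and grade POPF and other complications". On who fills it in and when, the plan says: "This form will be completed by the study coordinator on the day of discharge +/- one day". The form is completed again at any re-discharge, at outpatient visits and at about 90 days. On the mode of collection: "This information will be collected either over the telephone.or in person".

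Blinding (section 4c): "This will not be a blinded trial". That is the whole entry, although the item asks for a justification of blinding or not blinding. Masking of outcome assessment is not treated separately.

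Resources (section 10): "No additional staff will be acquired for this project". Salary support for the study coordinator is listed as a cost.

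The documents do not name the person who assigns the ISGPS grade. They mention no masked assessor, no adjudication and no written grading rule. The form is in the appendices, which are not in the text available for this review.

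**The concern.** The endpoint is a classification, and someone has to decide whether a fistula is present and which grade it has. The Abstract predicts fewer clinically significant fistulae and infectious complications with the non-suctioning drain. If the person who classifies knows the drain and the expected direction, borderline cases can be resolved differently in the two arms. Randomisation balances the patients but not the way their outcomes are read. A larger sample does not dilute the effect; it makes a biased difference more likely to reach significance.

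The decision to stop early is also exposed. Study Statistics plans an interim analysis after 150 patients and ends the trial early if the groups differ significantly. Classification that favours one arm could therefore contribute to early termination as well as to the final result.

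**Working it through.** **Inputs from the plan (Study Statistics, item c).** POPF 30% in the control arm ("The incidence of either POPF after DP is approximately 30" per cent) and 15% in the treatment arm; two-sided α = 0.05; power 0.80; 134 per arm.

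**Step 1: reproduce the plan's sample size.** With p1 = 0.30, p2 = 0.15 and p̄ = 0.225:

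n0 = [1.96·√(2·0.225·0.775) + 0.8416·√(0.30·0.70 + 0.15·0.85)]² / 0.15² = (1.1575 + 0.4889)² / 0.0225 = 120.5, so 121 per arm without continuity correction.

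With the correction, n = (n0/4)·[1 + √(1 + 4/(n0·0.15))]² = 133.5, so 134 per arm. This matches the plan. Masked grading does not change this number.

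**Step 2: effect of under-counting in one arm.** The under-counting fraction f is an assumption; the documents give no figure for it. Suppose there is no true difference: 30% in both arms, which is 0.30 × 134 = 40.2 expected cases per arm. In one arm a fraction f of the cases is not counted, so its observed rate is 0.30·(1 − f). The rejection probability is the sum of the two binomial distributions (134 per arm) over all outcomes where the two-sided pooled z test is significant at 5%.

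| f | Observed rate | Cases not counted (40.2·f) | False-positive rate, no correction | With continuity correction |
|---|---|---|---|---|
| 0 | 30.0% | 0 | 5.0% | 3.7% |
| 5% | 28.5% | 2.0 | 5.9% | 4.4% |
| 10% | 27.0% | 4.0 | 8.5% | 6.5% |
| 20% | 24.0% | 8.0 | 19.9% | 16.1% |

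A normal approximation of the uncorrected test gives 5.8%, 8.4% and 19.7% for the last three rows, so the result does not depend on the method.

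**Step 3: where the excess falls.** Without correction, the chance of a false finding in favour of the under-counted arm is 2.5% at f = 0, 7.9% at f = 10% and 19.8% at f = 20%. Nearly all the added error lies in one direction.

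**Step 4: what the text supports about the grader.** Section 4b gives the coordinator the task of completing the form and gives the form the purpose of supporting detection and grading. It does not connect the two by saying that the coordinator assigns the grade. Section 4c rules out blinding in general, and no other section restores it for outcome assessment. What is established is therefore an unnamed grader, a form completed without masking, and no masking at grading.

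**The case against.** The strongest reply is that the plan already limits discretion. It uses a published, graded definition, one standardised form for both arms and fixed collection times. The unseen form may already list the individual facts and contain a grading rule. This is fair: it may make the bias small, but it does not hide the arm from anyone.

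A second reply is that the numbers are only illustrative. This also stands. At 5% under-counting the inflation is slight, and with the continuity correction, which is the version that reproduces the plan's 134, the rate stays below the nominal 5%. The model also removes a share of all POPFs, whereas the mechanism concerns borderline cases only.

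A third reply is that masking the grading leaves earlier bias in place, because clinicians who see the drain make the care decisions that feed the grade. That is correct and limits the benefit. Classification is still a step that can be masked without changing care.

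A reader might go further than the documents allow in three ways:
- **The coordinator grades POPF.** The documents never say so.
- **The grade can certainly be derived from the existing form.** Its fields cannot be checked here, and some of them may reveal the drain.
- **Masked grading would be free.** Section 10 says only that no staff will be added, and it gives no workload.

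**Conclusion.** The point holds in limited form. In an open-label trial with a directional hypothesis, the primary endpoint rests on a form completed by someone from whom nothing hides the arm. The grader is not named, no masking is described at grading, and no justification is given. This is a weakness in how the primary endpoint is ascertained. It is not evidence that results will be biased, and it does not affect the sample size.

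The size of the effect is unknown. Under the assumptions shown (true rate 30% in both arms, 134 per arm, under-counting in one arm only), it ranges from negligible when about two cases are missed to roughly a fourfold false-positive rate when about eight are missed. The change is worth making because it leaves visits, procedures and patient care as they are.

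**What to change.** Keep the trial open-label and add the following to sections 4b and 4c and to Study Statistics:

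1. State who assigns ISGPS presence and grade of POPF.
2. Make sure that the form records the individual facts the ISGPS definition uses, and not only a conclusion.
3. Derive presence and grade by a written rule from a data extract without allocation or drain-type fields. Do this before allocation is merged, and before the 150-patient interim analysis for the patients included in it.
4. Have unclear cases settled from the same extract by existing team members who did not operate on that patient.
5. If masked grading is declined, give the reason under section 4c.

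**Cost.** Writing the rule, preparing the extract and reviewing unclear cases take some existing team time; the documents do not allow an estimate of how much. No new staff, visits or procedures are needed. Masking will be partial, because care decisions are made by clinicians who see the drain and some recorded facts may reveal it. The report should say so.
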